8.7 Blinding

The follow up data will be routinely collected online using the website/EDC system (and the reminders for this will be sent out automatically by email from the EDC system). This will prevent the follow up results being affected by the site researcher. Trial researchers who will be blind to treatment allocation include the Chief Investigator and Trial Manager. The Trial Manager will be in direct contact with participants to answer technical queries. The trial therapists will be unblinded and will be in direct contact with participants to follow up risk. It is possible that a site researcher could become unblinded during those (infrequent) conversations if the participant mentions details of the intervention and this will be recorded as part of the feasibility focus.

Should a blinded site researcher become unblinded then this will be logged as an unblinding and any telephone-based chasing of follow up data for that participant in future will be conducted by another blinded researcher at the site (if available). Therefore, only blinded site researchers will attempt to collect the primary outcome measures by telephone if the participant is unwilling to use the screening website for this purpose. Unblinded site researchers will not discuss information relating to condition with blinded site researchers. During any contact with participants the blinded site researcher will remind them not to divulge to which condition they were allocated. In the event that there are no

unblinded researcher at a site and telephone collection of follow up primary outcome is possible, this data will be collected, but will be logged and clearly marked as 'collected unblinded'. This will allow the statisticians to control for this in their analysis. The statisticians will be blinded to intervention until the analysis is done and they are interpreting the results.

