8.10 Trial assessments

Assessment will take place at baseline (start of treatment) and then at 6 weeks post baseline (equating to end of treatment) and 12-weeks post baseline. The 3-month follow up will be the primary endpoint. All assessments will be through EXCTU managed EDC system. Only if participants have not responded to email and text prompts to complete their follow ups at 6 and 12 weeks will they be contacted by phone and asked to provide the primary outcome measures only on the telephone. The results of the assessments are only to collect research data for the trial and will not be provided to medical practitioners. The only exception to that would be if a participant indicates suicide risk and asks us to provide their assessment results to their medical practitioner. They would need to give written consent for this and provide us with the contact details to do so. See risk protocol in Appendix.

At the end of treatment, participants that have received the sbLICBT resiliency intervention will receive an email asking them to participate in an acceptability focus group and Section 12 of the protocol provides further information on this.

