10.2 Outcome measures (Appendix 2)

Table 10 Outcome measures

Measure	Description	Reliability and Validity
SECONDARY OUTCOMES		
Brief Resiliency Scale (BRS; Smith et al., 2008)	6-item participant rated questionnaire assessing ability to on a 5 point scale for each item with anchors —Strongly Agree and Strongly Disagree. Items 1, 3, and 5 are positively worded, and items 2, 4, and 6 are negatively worded. Scored by reverse coding items 2, 4, 6 and adding responses varying from 1-5 for all six items giving a range from 6-30 with total divided by number of questions answered. Interpretation: Low Resiliency=1-2.99; Medium Resiliency=3-4.30; High Resiliency=>4.31.	Commonly adopted measure of resiliency and has been used to rate resiliency in a large number of populations (e.g. University students; cancer) across many countries (e.g. UK, China, Brazil, Germany). Adequate test-retest reliability (.69) with good internal consistency Internal consistency was good, with Cronbach's α ranging from 0.80-0.91 across four populations varying in age. Within the two University student populations Cronbach's α = 8.84-0.87.
Patient Health Questionnaire-9 (PHQ-9; Kroenke et al., 2001)	9-item participant rated questionnaire assessing frequency of symptoms of depression over the last 2 weeks. 4-point scale for each item, with anchors at 0=not at all, 1 = several days, 2= more than half the days, 3 =nearly every day. Unidimensional scale. Available in English, Spanish, German, and Dutch versions.	Leading measure of depression widely used in clinical trials, clinical practice, and as part of the NHS Quality and Outcomes Framework (QOF) for UK primary care, and Improving Access to Psychological Treatments (IAPT) Minimum Data Set (MDS). Cronbach's α =0.89 in primary care, test-retest reliability (ICC) 0.84 after 48 hours. Validation studies indicate positive correlations with measures of functional status (r=0.73), disability days (r=0.39), and symptom-related difficulty (r=0.55) At cut-off of \geq 10, excellent specificity (0.88) and sensitivity (0.88) with diagnoses of major depression by structured interview, replicated in a UK population (sensitivity 0.80; specificity 0.92).

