12.5 Primary analysis

Outcomes related to study feasibility and intervention acceptability (see Table 9 and Table 10).

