12.6 Secondary analyses

12.6.1 12 week post baseline follow-up comparison

Primary (BRS) and secondary (PHQ-9; GAD-7, WSAS) outcomes will be compared at 12 week follow-up using the statistical approach outlined above.

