As part of our policy for addressing risk and prioritising the welfare of participants, participants are provided with links to online support, access to contact the trial team, and automatic signposting to help and guidance if reporting risk (e.g., suicidal thoughts, as indexed in items within outcome measures such as the Patient Health Questionnaire-9, PHQ-9 on the screening or follow-up websites) or levels of symptoms suggesting a need for help within any of the assessments within the cohort study. These messages include general information on the presenting symptom, recommended actions to make themselves safe, and advice to seek medical help, and direct links to relevant national sources of help.

The main indicators of harm will be the completion of questionnaires by the participants at all assessments (baseline, 6 weeks, 12 weeks). Questionnaires will be automatically screened for signs of severe distress (for example, defined as scores above 20 on PHQ-9 for depression or reports of suicidal ideation), with automatic programmed questions following up to ascertain aspects of risk and to automatically provide users with recommended advice and signpost towards help (family doctor, local hospital, relevant charities; e.g., website link to the Samaritans in the UK. Other indicators would be report of worsening symptoms or suicidality in direct contact from participants to the research team. Individuals reporting severe levels of symptoms or meeting diagnostic criteria for depression will be offered guidance to seek appropriate help from their GP/family doctor, occupational health or student well-being service should this seem necessary.

For those who enter the trial and then indicate risk there will be the option to contact a site researcher via e-mail or telephone to seek advice. This advice will include guidance to seek appropriate help from their GP/family doctor, occupational health or student well-being service should this seem necessary. Project researchers will be trained in and provided with a protocol to assess risk and with standard useful responses in these circumstances (see Section 14 on Risk Management). The trial site has a designated senior clinician [clinical psychologist or CBT Therapist] who will be available as a resource to researchers to provide guidance on clinical issues arising from participants either through

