13.2 Definitions

Standard definitions for adverse events etc are in the table below. Because the current interventions are digital self-help rather than a medicinal product and involve no biological agent, it is not appropriate to define adverse events etc re any untoward medical occurrence – rather as a psychological intervention, appropriate adverse events would include those related to mental state and behaviour:

- i) Serious adverse events (SAEs) including death, suicide attempt, self-harm, serious accident or violent incident, referral to crisis care or admission to psychiatric hospital.
- ii) Adverse Events (AE) may include significant worsening symptoms of anxiety, worsening symptoms of depression, as operationalized by a reliable deterioration of movement from 'mild' to 'severe' or 'moderate' to 'severe' levels of symptoms on GAD7 or PHQ9 AND a change of ≥4 points on GAD7 or ≥6 points on PHQ9 from baseline assessment to 6 weeks assessment or from 6 weeks assessment to 12 weeks assessment, new instance of self-harm, new instance of suicidality.

The following definitions are therefore adapted in light of this – see **Table 12**.

Table 12 Definitions of Events

Term	Definition
Adverse Event (AE)	Standard: Any untoward medical occurrence in a participant to whom a medicinal product has been administered, including occurrences which are not necessarily caused by or related to that product. Adapted: Any deterioration in mental state or behaviour in a participant to whom the intervention has been administered, including occurrences which are not necessarily caused by or related to the intervention.

Adverse Reaction (AR)

Standard: An untoward and unintended response in a participant to an investigational medicinal product which is related to any dose administered to that participant.

The phrase "response to an investigational medicinal product" means that a causal relationship between a trial medication and an AE is at least a reasonable possibility, i.e,. the relationship cannot be ruled out.

All cases judged by either the reporting medically qualified professional or the Sponsor as having a reasonable suspected causal relationship to the trial medication qualify as adverse reactions.

Adapted: An untoward and unintended response in a participant to an intervention which is related to any dose of the intervention administered to that participant.

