13.3 Recording and reporting of SAEs, SARs AND SUSARs

[figure not shown]
All serious adverse events that are trial or treatment related will be recorded and immediately reported to the Chief Investigator and within 1 working day (24 working hours) to the ExeCTU Trial Manager. If these are also classed as unexpected, they will be reported to the relevant ethics committees.

We will, in line with other complex intervention studies, monitor non-serious adverse events, serious adverse events that are not trial or treatment related, serious deterioration, and active withdrawals from treatment, with specific questions in the follow-up and in response to specific participant-initiated reports. Symptoms of depression or anxiety will not be defined as adverse events unless suicidal ideation, plans or an attempt has been made. The reporting period for all events and reactions will be from referral to 12weeks post baseline follow-up. Data on any adverse events will be collected by a member of the research team at each assessment and entered directly into the EDC.

The SAE form will capture the following data:

- Date and time of onset
- Date and time investigator became aware
- SAE category
 - o Death i.e. (homicide, suicide, accident, illness, all appropriate options) etc.)
 - Life threatening i.e. (suicide attempt, serious assault, self- harm)
 - o Hospitalisation or prolongation of existing hospitalisation or referral to crisis team
 - Persistent or significant disability or incapacity i.e. (include development of problematic substance/ alcohol abuse; onset of new Axis I disorder)
 - Congenital anomaly or birth defect
 - Other i.e. (potentially dependent life events, e.g. job loss divorce)
- The intensity will be specified as mild, moderate or severe
- The SAE will be determined as intermittent or continuous
- The SAE will be determined as expected or unexpected
- The SAE outcome will be determined as resolved with a date provided, resolved with sequelae, ongoing (follow ups to the SAE will be provided when there is a change to report in participants condition) or died (if died the cause of death will be specified)
- The SAE relationship to the study or trial procedures will be determined as not related, unlikely to be related, possibly related, definitely related or unknown
- A detailed description of the event will be provided and this field will also be used to
 document the dates and number of attempts made to contact a participant by phone and/or

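### Telephone follow-up is limited to the primary outcome measures, so PHQ-9 and GAD-7, on which systematic harm detection rests, are lost for participants reached by telephone

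*Protocol*

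**What the plan says.** Protocol 8.10 (Trial assessments) makes the telephone a last resort at 6 and 12 weeks. Participants who have not answered email and text prompts are "contacted by phone and asked to provide the primary outcome measures only on the telephone". Section 8.7 (Blinding) describes the same call: "only blinded site researchers will attempt to collect the primary outcome measures by telephone if the participant is unwilling to use the screening website".

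The protocol uses *primary* in more than one way:

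- 12.5 gives the primary analysis as "Outcomes related to study feasibility and intervention acceptability (see Table 9 and Table 10").
- 12.6.1 states "Primary (BRS) and secondary (PHQ-9; GAD-7, WSAS) outcomes will be compared at 12 week follow-up".
- Table 10 in 10.2 places BRS, PHQ-9, GAD-7 and WSAS together under "SECONDARY OUTCOMES".

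The safety sections assume that the symptom scales are available at every visit:

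- 13.1: "The main indicators of harm will be the completion of questionnaires by the participants at all assessments (baseline, 6 weeks, 12 weeks"). They are screened automatically for PHQ-9 above 20 or suicidal ideation.
- 13.2 counts as an adverse event a shift into the severe band together with "a change of ≥4 points on GAD7 or ≥6 points on PHQ9 from baseline assessment to 6 weeks assessment", or the same change from 6 to 12 weeks.
- 13.3: "Data on any adverse events will be collected by a member of the research team at each assessment and entered directly into the EDC".
- The procedures schedule in 8.11 marks both depression assessment and adverse-event assessment as due at 6 and at 12 weeks.
- 14.3.2 triggers risk questions R1 to R3 from PHQ-9 item 9 and uses the resulting records to follow the frequency of suicidality in each arm.

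**The concern.** The people who get a telephone call are those who ignored earlier prompts. Some of them may have disengaged or become worse, so they are a group in which harm data matter. Read literally, 8.10 has the caller collect an outcome measure and leave out the scales on which 13.1, 13.2 and 14.3.2 rely. Harm data would then be absent in a group that may differ from online completers. The comparison of suicidality between arms would cover online completers only, and the cumulative evidence of harm on which 12.7 bases discontinuation of the trial would be thinner than the safety section implies. The trial is also meant to test follow-up procedures before any definitive trial, so a gap here could be carried forward.

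**Working it through.** The protocol gives no figure to reproduce. The check compares the sections, then sizes the gap under stated assumptions.

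**1. Are PHQ-9 and GAD-7 in the call?** Take each use of *primary* in turn.

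| Source | What is primary | PHQ-9 and GAD-7 in the call? |
|---|---|---|
| 12.5 | Feasibility and acceptability | No; most feasibility outcomes are counts that a participant cannot supply |
| 12.6.1 | BRS | No; named as secondary |
| Table 10 | No scale; all four are secondary | No |

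No section labels either scale primary.

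**2. Which safety functions need them?**

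| Function | Needs | Available after a telephone completion under 8.10? |
|---|---|---|
| Main harm indicator (13.1) | Questionnaires, PHQ-9 total | No |
| Score-based adverse event (13.2) | PHQ-9 and GAD-7 at two consecutive assessments | No; a missing 6-week score breaks both comparisons, a missing 12-week score breaks the second |
| Suicidality by arm (14.3.2) | Item 9, then R1 to R3 | No |
| Adverse-event questions (13.3, 8.11) | A team member asking | Still required by 13.3, but not mentioned in 8.10 or 8.7 |

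**3. How many participants?** The planned total is 120 with 1:1 allocation (8.4, 8.6), so 120 / 2 = 60 per arm. The share followed up by telephone is not stated. Assume f = 15% to 30% at a visit:

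- 60 × 0.15 = 9 per arm
- 60 × 0.30 = 18 per arm

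**4. Why the coding of the gap matters.** This is an illustration only. Assume an event rate of 10% in online completers and 20% in those telephoned, with no such event picked up on the call. The true rate is 0.10(1 − f) + 0.20f.

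| | f = 0.15 | f = 0.30 |
|---|---|---|
| True rate | 0.085 + 0.030 = 0.115 | 0.070 + 0.060 = 0.130 |
| Observed rate if the gap is coded missing | 0.100 | 0.100 |
| Relative understatement | 0.015 / 0.115 = 13% | 0.030 / 0.130 = 23% |
| Observed rate if the gap is coded no event | 0.085 | 0.070 |
| Relative understatement | 0.030 / 0.115 = 26% | 0.060 / 0.130 = 46% |

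The last row is also the share of all events that fall in the telephone group. On these inputs, coding the gap as no event doubles the understatement.

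**The case against.** Several points on the other side have force.

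*Adverse-event questions.* A reader might infer that the call drops them and that 8.10 and 13.3 cannot both be followed. The text does not support that. The restriction in 8.10 concerns outcome measures; adverse-event assessment has its own row in the schedule, 13.3 requires it at each assessment with no telephone exception, and 13.4 has researchers check for events at follow-up. A caller could do both. What stands is that 8.10 gives no instruction to do so.

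*Other routes to harm data.* A reader might also infer that harm goes unmeasured in this group. That too goes beyond the documents: 13.1 accepts direct reports of worsening or suicidality, and 14.8 gives a telephone risk script. These routes are weaker, though. Reports have to be volunteered, the script's risk questions follow something the participant has said or written, and the 13.4 check may be prompted by website feedback that these participants have not generated.

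*Meaning of primary.* Because 12.5 points to Table 10, one could argue that all four scales belong to the call. But that table heads them all as secondary, and on this reading the word *only* would have little left to exclude. The argument mainly confirms that the content of the call is not fixed.

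*Status of the scales.* 13.3 says that symptoms of depression or anxiety are not adverse events unless there are suicidal thoughts, plans or an attempt, which conflicts with 13.2. The gap matters under either rule, since item 9 and R1 to R3 are what detect that exception.

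*Burden.* A short fallback is a common and reasonable trade-off, and the call adds data from people who would otherwise give none. Nothing in the protocol says that a telephone contact is counted as a complete assessment, and the feasibility table reports item-level completion in the intervention arm, where partial data would show.

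**Conclusion.** The point holds as a conflict between the telephone rule and the safety sections. Followed as written, 8.10 and 8.7 leave out PHQ-9, including item 9, and GAD-7 for telephone completers, and so remove systematic symptom-based harm detection at that visit. They do not remove all ascertainment of harm, and they do not cancel the adverse-event collection required by 13.3.

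The size depends on a telephone share that the protocol does not give. At an assumed 15% to 30%, 9 to 18 of 60 participants per arm would be affected at a visit. The event rates in the illustration are also assumed, and it takes no such event to be found on the call, which the remaining routes make too pessimistic. It shows the direction of the error and the importance of coding, not an expected bias.

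**What to change.** In 8.10 and 8.7, replace the restriction to primary outcome measures with a named telephone set that agrees with 8.11, 13.1, 13.2 and 13.3:

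1. BRS first.
2. PHQ-9 and GAD-7 next.
3. The adverse-event questions that 13.3 already requires, asked last so that the scales are scored before an answer can reveal the allocation to the caller.

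State that any harm item not obtained is recorded as missing, not as no event. Naming the scales also settles what the call contains, whichever meaning of *primary* is kept elsewhere.

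The web sequence of risk questions in 14.3.2 and the telephone script in 14.8 differ, and both could apply to these calls. The trial team must reconcile the two passages; no particular risk rule is proposed here. The conflict between 13.2 and 13.3 on whether symptom change is an adverse event should be reconciled at the same time.

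The cost is a slightly longer call, for non-responders only, some of whom may answer less completely. Placing BRS first limits the loss on that scale. Section 14.7 already requires staff with telephone contact to be trained in the risk procedure.

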8.11 Long term follow-up assessments

Participants will be followed up at 6 and 12 weeks post baseline.

Table 9 Procedures schedule

Procedures	Screening	Baseline	6 weeks post- baseline follow-up	12 weeks follow-up
Informed consent	Yes	Yes	No	Yes
Demographics	Yes	No	No	No
Mental Health History	Yes	No	No	No

Eligibility assessment	Yes	No	No	No
Randomisation	No	Yes	No	No
Access to intervention	No	Yes	Yes	Yes
Assessment of wellbeing and depression	Yes	Yes	Yes	Yes
Assessment of current functioning	No	Yes	Yes	Yes
Feasibility outcomes	No	No	No	Yes
Adverse event assessments	No	No	Yes	Yes

8.11.1 Payment

Participants will be paid in electronic vouchers for taking part in the 6 weekly measures and after completion of the 12 weeks follow up. We will pay £10 for completing the 6 weekly post-baseline assessments and the 12 weeks follow up.

Researchers will be able to run reports on the Exeter CTU database to identify which participants have completed follow ups at the key payment points (after 12 weeks). Site researchers will arrange for the payment of participants using electronic shopping vouchers, which can be emailed or sent by text or via direct bank transfers. No travel expenses are anticipated for participants as all assessment and intervention contents are provided remotely via digital platforms (website, app).

8.12 Withdrawal criteria

Participants can choose whether they want to stop using the sbLICBT intervention, or if they want to withdraw from the trial completely (including all assessments) at any time. Participants will also be withdrawn from the trial if the site clinical advisor, or the participant's medical practitioner advises that this is best for their wellbeing. A log will be kept of the participant number, reason for and date of all withdrawals from the trial. Participants who met the inclusion and exclusion criteria at baseline will not be replaced. Participants who did not meet the criteria at baseline can be replaced and their data removed from the data set. Participants who withdraw from the trial will not be followed up. Once a participant withdraws, all email and text notifications that are set on auto will be removed.

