6.1 Patient registration/randomisation procedure

At the point of randomisation participants will be automatically registered on to the trial using the electronic data capture (EDC) system. Randomisation is after the online consent, the screening process and after the online baseline assessment. There is a two-part consent process which in the first part asks for permission to screen and take part in the assessment. The second part of consent with agreement sought to take part in the study is taken prior to baseline assessment. Participants can stop the assessment at any stage and be emailed a link to return the screening website. this allows them to have time to consider the participant information which they have read on screen and which is emailed to them. The email link will be live for 14 days. After this time the participant will need to contact the site to ask for the link to be reset.

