8.2 Screening

Participants will be screened by an EDC system set-up and managed by Exeter CTU for university students - those under 16 will automatically be screened out pre-assessment. Website users who report having current risk will be taken to the feedback screen where they will be advised that we are sorry to hear that they are feeling that way, to please contact their GP and to give them sources of online help and support.

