8.6 Method of implementing the randomisation/allocation sequence

Participants will be randomised by a web service which interfaces with the EXCTU EDC system and database. This will be an automated process. The EXCTU database will send an unblinded team member (administrator/therapist) indicating when an individual [by study ID] has been randomized to the active intervention. This team member will then access the relevant details in the EXCTU database and manually set up the participant in the internet platform using administrator rights via the internet platform dashboard. A system automated email will be sent to the participant indicating the condition to which they are randomised, informing them what to expect, date of sbCBT group to next intervention arm and asking the participant to confirm receipt by return of email to unblinded team member. The team member will send up to 6 reminder emails to any participant that has failed to confirm receipt.

Failure to receive confirmatory email: the relevant unblinded team member will also be able to monitor if the participant has accessed the intervention and check if there are any difficulties and encourage to sign-up.

Detailed procedure for randomisation:

- 1. Participants are block randomised (30 participants per arm) into the 2 arms (DTC control versus sbLICBT) on an intention-to-treat basis.
- 2. Block randomisation will continue until 120 participants (6 iterations of 60 participants) are randomised.
- 3. The system must record the allocation and the date randomised.
- 4. The trial manager and at least one other researcher remain blind to the allocation; the participant will be aware of which intervention received. The practitioner / administrator will be unblinded in order to set-up participant on internet platform.
- 5. On successful randomisation, a finish page is displayed with a message telling the participant to look for an email message from the trial team.

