9 INTERVENTIONS

9.1 Written Strength-Based Low-Intensity CBT (SBLICBT) Resiliency Intervention with Support on Demand

The intervention is reported according to the Template for Intervention Description and Replication (TIDieR) Checklist (Hoffman et al., 2014).

Table 8 TIDieR Checklist

Item	Description
Brief Name	Bounce Back: Finding Your Inner Strength
Why	As a consequence of being exposed to increasing demands presented by University life, students now have an increased likelihood of experiencing mental health difficulties resulting in long-term disadvantage. Enhancing resiliency to enable students to cope when facing such demands has potential to prevent the development of mental health difficulties. A protocol for a strength-based CBT intervention (Padesky & Mooney, 2012) has informed the development of a written low-intensity CBT intervention. To enhance resiliency, the participant engages with the written intervention to work through four-steps –(1)Record a successful regular activity, (2)Build a personal model of resiliency, (3)Apply personal model of resiliency to an area found challenging, (4)Practice resilience.
What	Written strength-based low-intensity CBT intervention with an initial 60-minute didactic group session to provide an overview of the resiliency intervention and introduce availability of 'on demand' support. On-demand support will be available face to face, virtual, phone or by email for up to 6 weeks.
Who Provided	A Psychological Wellbeing Practitioner (PWP) trained to support the intervention with supervision provided.
How	Following a 60-minute didactic group session where the intervention introduced, participants will be encouraged to engage with the written CBT self-help intervention over the following 6 weeks. 'On demand' minimum contact 'Plan-Do-Review' support will be available on request, over face to face or by email.
Where	University of Exeter.

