12.4 Summary of baseline data and flow of patients

The analysis and presentation of the trial will be in accordance with CONSORT guidelines (Schulz et al., 2010). Recruitment, intervention uptake, outcome completion rates and attrition will be reported (with 95% Cls) and shown on a flow diagram.

Premature discontinuation of intervention may be instigated by the participant or investigator. Participants may elect to withdraw from the study if they wish to do so at any time and for any reason (including perceived harms or lack of efficacy of intervention). Researchers may also request that trial intervention be discontinued for reasons of participant safety at any time; such requests will be made to and approved by the PI or an appointed deputy where possible.

Participants will be withdrawn from the study entirely if discovered as ineligible at the time of recruitment. As a self-help psychological intervention, we do not anticipate significant iatrogenic effects or side-effects requiring individual discontinuation. Participants who elect to discontinue their allocated intervention will be requested to continue to provide outcome data. If a participant wishes to withdraw from the study entirely (and not provide further follow-up data) we will ask them if they are happy to allow us to retain the data already provided to the trial; if the participant does not consent to retention of data, the data will be destroyed.

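### Randomised participants later found ineligible may be withdrawn, removed from the data set and replaced, which conflicts with intention-to-treat and unsettles the feasibility counts

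*Protocol*

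**What the plan says.** Two places in the protocol deal with ineligibility that comes to light late.

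- Section 8.12 (Withdrawal criteria) separates two groups. For eligible participants: "Participants who met the inclusion and exclusion criteria at baseline will not be replaced". For the others: "Participants who did not meet the criteria at baseline can be replaced and their data removed from the data set".
- Section 12.4 (Summary of baseline data and flow of patients) states: "Participants will be withdrawn from the study entirely if discovered as ineligible at the time of recruitment".

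The timing is fixed in Section 6.1: "Randomisation is after the online consent, the screening process and after the online baseline assessment". Section 8.3 describes the same order, with randomisation following completion of the baseline measures. Eligibility is judged online and in the same way for everyone (Section 8.2: "Participants will be screened by an EDC system set-up and managed by Exeter CTU for university students").

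The governing principle is stated once, in Section 8.6: "Participants are block randomised (30 participants per arm) into the 2 arms (DTC control versus sbLICBT) on an intention-to-treat basis".

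**The concern.** Removing people after randomisation because of something learned later is safe only if the chance of learning it, and the decision to act on it, are unrelated to the arm. The protocol gives no such assurance. It does not confine removal to what the screening and baseline records show, sets no time limit, and does not say who decides or whether that person is blind to allocation. The wording in Section 8.12 is permissive, so each removal is a choice.

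Contact differs between the arms early on. In the sbLICBT arm there is a group session, and Section 9.1 adds: "On-demand support will be available face to face, virtual, phone or by email for up to 6 weeks". The practitioner and administrator know the allocation (Sections 8.6 and 8.7). A past history of psychosis, mania or dependence is self-reported at screening, so a missed case could come out in such contact. Under Section 9.2 the delayed-treatment arm (DTC) has no intervention contact until the first arm's six weeks are over.

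Two things are at stake. One is the between-arm comparison of BRS, PHQ-9, GAD-7 and WSAS, which is meant to inform a later definitive trial. The other is the primary feasibility result: Section 10.1 lists numbers randomised and numbers completing each assessment as feasibility outcomes, and Section 12.5 makes feasibility the primary analysis.

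**Working it through.** **1. Does the rule reach randomised people?** Someone screened out online never reaches the second consent form or randomisation (Section 8.3), so there is nobody to withdraw or replace. A participant who is discovered to be ineligible, withdrawn and replaced has therefore normally been randomised. The exclusions are post-randomisation.

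**2. Do the passages agree?** No. Section 8.6 commits to intention-to-treat. Section 8.12 permits removal from the data set and replacement. Section 12.4 makes withdrawal mandatory. Section 8.12 adds that those who withdraw are not followed up. If that is applied here, outcomes after the discovery are never collected.

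**3. Counts.** The target in Section 12.2 is 2 × (30 + 30) = 120, or 60 per arm, which matches the stated sample size. (The iteration counts elsewhere do not: 6 × 60 = 360 in Section 8.6 and 3 × 60 = 180 in Section 9.1. That is a separate matter; I use 120.) Section 8.6 stops when 120 have been randomised. With k participants removed, stopping there leaves 120 − k in the data set, whereas replacing them means randomising at least 120 + k. For k = 6 that is 114 in the data set, or at least 126 randomised. Either way the two counts part.

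**4. Possible size of bias.** The protocol gives no effect size, SD, ineligibility rate or detection rate, so every input here is an assumption. Let p be the share of randomised participants who are ineligible, d their deficit in SD, and q the share of them detected and removed. With no treatment effect,

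arm mean = −d·p·(1 − q) / (1 − p·q),

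and the spurious difference is the sbLICBT mean minus the DTC mean. A positive value favours sbLICBT.

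Example: p = 0.15, d = 1.0, detection 0.8 in sbLICBT and 0.1 in DTC.
- sbLICBT: −0.15 × 0.2 / (1 − 0.12) = −0.034
- DTC: −0.15 × 0.9 / (1 − 0.015) = −0.137
- Difference: 0.103 SD

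| Detection, sbLICBT v DTC | p = 5%, d = 0.5 | p = 15%, d = 1.0 |
|---|---|---|
| 0.5 v 0.5 | 0.000 | 0.000 |
| 0.5 v 0.1 | 0.010 | 0.056 |
| 0.8 v 0.1 | 0.017 | 0.103 |
| 1.0 v 0.0 | 0.025 | 0.150 |

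In the last row, 3 and 9 of 60 respectively are removed from sbLICBT and none from DTC.

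For scale, the 95% confidence interval half-width at 60 per arm is 1.96 × √(2/60) = 0.36 SD.

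**5. After the fix.** If everyone stays in the allocated arm, this source of bias is zero by construction.

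**The case against.** The strongest reply is that eligibility is a baseline fact. Screening is automated and identical in both arms, and PHQ-9 and GAD-7 are measured again at baseline, before allocation. A breach visible in those stored records can be found equally often in either arm, and excluding on such facts, judged blind, need not bias anything. This is correct, but the protocol does not restrict removal to those records or require blind judgement.

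A reader might go further and infer that removal will fall mainly on sbLICBT and strip that arm of its more unwell members. The documents do not support that. The group session is didactic and support is on request. Apart from the final DTC group (Section 9.1), DTC participants receive the intervention after week 6, within the 12-week follow-up. Contact about risk (Section 8.7), telephone follow-up (Section 8.10) and adverse-event assessment (Section 8.11) are not limited to one arm. Unequal removal is possible, not shown.

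A reader might also take the data to be destroyed and the number of screening errors lost. Neither follows. Section 8.12 speaks of removal from the data set; destruction is stated only for a withdrawing participant who refuses retention (Section 12.4). Section 8.12 also requires a log of all withdrawals with reasons, and Section 8.6 requires the allocation to be recorded. The count is recoverable, although Section 10.1 does not ask for it by arm.

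Finally, the intention-to-treat phrase sits in a randomisation procedure, and analysis sets are usually left to the SAP. That would answer a complaint about missing detail. Here the protocol itself fixes a rule on removal, and an analysis set defined later cannot include outcomes that were never collected.

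**Conclusion.** The point stands as a conflict between Sections 8.12 and 12.4 on one side and Section 8.6 on the other. People already randomised may be withdrawn, removed from the data set and replaced, at discretion and without safeguards against removal that depends on arm.

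The resulting bias cannot be sized from the protocol. It is zero with equal detection and about 0.02 to 0.15 SD under strongly unequal detection (0.8 v 0.1, up to the extreme 1.0 v 0.0), with an assumed 5 to 15% ineligible and an assumed deficit of 0.5 to 1.0 SD. All of that lies well inside the 0.36 SD half-width. The larger deficit may be generous, since someone who concealed only a past history still scored 9 or below on PHQ-9 and GAD-7. It is tempting to express the bias as a share of the treatment effect, but Section 12.1 gives no effect size, so no such percentage is supportable.

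The arm comparison is secondary and exploratory. The effect on the counts is more direct, because they belong to the primary outcome. The text should be corrected, but the point does not undermine the trial.

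**What to change.** In Section 8.12, replace the sentence on replacement and data removal; in Section 12.4, replace the sentence on withdrawing ineligible participants. Suggested content for both:

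> Every randomised participant stays in the data set, the flow diagram and the analysis, in the allocated arm. Participants found after randomisation to be ineligible are asked for outcome data like all others, unless they themselves withdraw or refuse retention of their data (Section 12.4). Nobody is replaced. Ineligibility found after randomisation is logged and reported by arm as a feasibility outcome. Any exclusion on this ground is confined to a sensitivity analysis that uses only records made before randomisation, judged by someone blind to allocation.

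Add a matching line, by arm, to the feasibility table in Section 10.1 and Appendix 1. Whether an ineligible person continues the intervention is a separate clinical decision, and it should not settle what happens to their data.

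The cost is two replaced sentences, one table line and a slight dilution of the comparison by a few ineligible participants.
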